1. STUDY OVERVIEW

1.1. Study Objective

To determine the impact of three selected warning labels versus a 'no label' control condition, on consumers' online alcohol purchase behaviour.

1.2. Study Design

A four-arm, parallel, randomised controlled trial, undertaken online.

Participants will be recruited via a market research company's (Dynata and partners) national online panel. Panel members are invited by email to take a web-based survey hosted by Dynata, which includes a hyperlink to a participant information sheet (which can be downloaded) on the study website. Interested participants will be asked to complete a series of online questions to ascertain their eligibility. The participant information sheet will also be available in Te Reo Māori.

Three different warning labels have been developed, based on findings from Stages 1 and 2 of the WARNING study, stakeholder feedback and published research. These labels relate to liver cancer, violence, and heart attack/stroke, and utilise both a pictogram/image with text (Figure 1).

Figure 1: Tested alcohol warning labels

Liver cancer	Violence	Heart / stroke
		

These labels will be shown on an alcoholic drink and beside the product and tested against a no-label control (i.e., the product will only display the mandatory pregnancy and % alcohol labels). Participants will have the choice to view the text of the test warning labels (shown in Figure 1) in English only, or English and Te Reo Māori.

1.3. Study Population

Participants will be adults (≥ 18 years); report purchasing and consuming any alcohol from an off-license retailer (e.g. supermarket, bottle store, uber eats, etc, but excluding drinking at a bar, pub, or restaurant) in the past week; are able to read English; have access to the internet, reside in NZ; and have not previously undertaken a Dynata survey about alcohol. Only people who have drunk beer, wine, spirits or ready-to-drink (RTD) products in the last week will be eligible

1.4. Sample size

A sample size of 1,000 participants (250 per arm) will have $>90\%$ power at the 5% overall significance level (two-sided) to detect an effect size of 0.33 Standard Deviations (SD) on the primary outcome, between any one of three label groups and the control, with adjustment for multiple comparisons. An approximately equal sample size per ethnic group will provide 90% power at 5% significance to detect a group difference of 0.5 SD in subgroup analysis.

1.5. Randomisation

Participants will be randomly allocated (1:1:1:1 ratio) within the Dynata platform to view an image of an alcoholic drink (based on their response to the 'drink of choice' question) with one of the three warning labels, or no warning label (control), on the product.

Randomisation will be stratified by ethnicity (Māori and/or Pacific; non-Māori/non-Pacific) and alcohol use (light to moderate; heavy) using block randomisation with variable block sizes of 4 or 8. The randomisation sequence will be generated by the trial statistician, and centrally managed by Dynata and concealed until the point of randomisation.

1.6. Blinding

Due to the nature of the study, participants will be aware of the treatment allocation post-randomisation. Study investigators and the trial statistician will remain blinded until the end of the trial.

1.7. Baseline Data

After screening, eligible participants will be asked to provide baseline data via the online platform. Baseline questions will include:

- **Socio-demographics:** Age group, sex, gender, ethnicity, whether they would classify their place of residence as 'urban' or 'rural', and highest educational level (as a measure of socio-economic position).
- **Existing health conditions:** Participants will be asked if they have ever been told by a doctor that they have any of nine listed health conditions. These conditions will be those where alcohol is a risk factor. This question is asked because participants with an alcohol-related health condition may respond to the questions in a different way and may be more likely to support mandated alcohol warning labels.
- **Voting behaviour:** (this is an outcome routinely collected by Dynata). This question is asked because it is possible that more conservative participants may be less likely to support mandated alcohol warning labels.
- **Alcohol use and misuse:** assessed using the AUDIT-C.
- **Drink of choice** (i.e., the drink they purchase most of and drink): Beer, wine, spirit, or RTD products.

- **Average ‘regular’, weekly number of alcoholic drinks purchased:** Participants will be asked to estimate their average, weekly number of alcoholic drinks purchased from an off-license retailer (e.g. supermarket, bottle store, uber eats, etc, but excluding drinking at a bar, pub, or restaurant).
- **Average ‘regular’, weekly spend on alcoholic drinks:** Participants will also be asked to estimate their average, weekly spend on alcoholic drinks purchased from an off-license retailer (e.g. supermarket, bottle store, uber eats, etc, but excluding drinking at a bar, pub, or restaurant).

1.8. Outcome Assessments

Primary outcome:

Participants will be asked about their ‘likely intent’ to purchase and drink the viewed alcoholic drink, based on an 11-point Juster probability scale, where zero represents ‘not likely at all to purchase and drink’ and 10 represents ‘very likely to purchase and drink’.

Secondary outcomes:

Participants will be asked to imagine that they are completing their regular, weekly shop for alcohol and to choose how many (from a drop-down menu of 0-100) of this particular alcoholic drink they would buy and drink. The participants will be advised to assume the drink is in the same price range as their usual drink of choice.

Participants will then proceed to the next page (without the ability to return/back-click), and will be asked a series of questions:

- **Unprompted recall:** Participants will be asked if they noticed anything about the image. Those who select ‘yes’ will be asked to explain their answer in a free-text field.
- **Prompted recall:** Participants will be asked if they noticed any warning labels (Yes/No).
- **Comprehension:** Participants will be asked to explain what message(s) the label(s) was providing. Answers will be collected using a free-text field.
- **Behaviour (unprompted):** Participants will be asked to explain what the label(s) was wanting them to do, with responses captured in a free-text field.
- **Behaviour (prompted):** Participants will be asked if the presence of the warning labels influenced the number of drinks they selected to purchase and drink in the previous section (assessed on a 5-point scale, where ‘1’ is ‘No, not at all’ and ‘5’ is ‘Yes, very much’). Participants will also be asked if they are likely to discuss the labels with family and/or friends (assessed on a 5-point scale where ‘1’ is ‘No, not likely at all’ and ‘5’ is ‘Yes, very likely’).
- **Judgement:** Participants will be asked if the message provided by the warning label(s) was believable, measured on a 5-point likert scale, where ‘0’ is ‘Not believable at all’ and ‘5’ is ‘Very believable’, and to explain their answer in a free-text field.

- Support for health warning labels: Participants will be asked how strongly they agree or disagree with the following statement: “Alcohol health warning labels should be required on all alcoholic drinks?” Responses will be measured on a likert scale of 1 to 7, where 1 is strongly disagree and 7 is strongly agree. Participants will also be asked to explain their response to the above question in a free-text field.

2. VARIABLE DEFINITIONS

2.1. AUDIT-C scores

For eligible participants, alcohol use will be assessed using the three AUDIT-C questions (see below) and sex at birth (male/female). The score for each question is indicated in the bracket.

Q1. How often did you have a drink containing alcohol in the past year?

- Monthly or less (1)
- 2-4 times a month (2)
- 2-3 times a week (3)
- 4 or more times a week (4)

Q2. How many standard drinks containing alcohol did you have on a typical day when you were drinking in the past year?

- 1 or 2 (0)
- 3 or 4 (1)
- 5 or 6 (2)
- 7 to 9 (3)
- 10 or more (4)

Q3. How often did you have six or more drinks on one occasion in the past year?

- Never (0)
- Less than monthly (1)
- Monthly (2)
- Weekly (3)
- Daily or almost daily (4)

A total score out of 12 will be calculated by summing the three AUDIT-C question scores. Higher scores indicate an increased likelihood of alcohol dependence.

Mild to moderate alcohol use is indicated by an AUDIT-C score of <3 for women and <4 for men, whilst **heavy alcohol use** is indicated by an AUDIT-C score of ≥ 3 for women and ≥ 4 for men. These two categories are used to define the stratification factor “alcohol use” in randomisation.

2.2. Prioritised ethnicity

Each participant will complete a question on which ethnic groups they belong to (tick all that apply):

- a. New Zealand European
- b. Māori
- c. Samoan

- d. Cook Islands Māori
- e. Tongan
- f. Niuean
- g. Chinese
- h. Indian
- i. Other, e.g., Dutch, Japanese, Tokelauan (please state): _____

Those who tick (b) and/or any of (c)-(f) will be in the ethnic group “Māori and/or Pacific”. Those who don’t tick any of these options will be in the ethnic group “non-Māori/non-Pacific”. These two categories are used to define the stratification factor “ethnicity” in randomisation.

For analysis purposes, we will also summarise Māori and Pacific participants separately. Those who tick (b) will be in the ethnic group “Māori”. Those who didn’t tick (b) but ticked any of (c)-(f) will be in the ethnic group “Pacific”.

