3.3. Efficacy Analysis

Treatment evaluation will be performed on the principle of intention-to-treat (ITT), including all randomised participants in the group they were randomised to. Since all eligible participants will receive the intervention and complete the questionnaire online, no per protocol analyses are planned.

The primary outcome will be analysed using linear regression model, adjusting for stratification factors (ethnicity and alcohol use) and the type of alcohol the participant chose (beer, wine, spirit or RTD), and controlling for multiple comparisons with the control group. Other baseline characteristics (e.g. sex and age group, pre-existing alcohol-related health conditions) will be considered in the model if deemed important. Model-adjusted mean difference between the groups will be estimated with 95% confidence interval and p-value.

As a pre-planned subgroup analysis, the consistency of intervention effects on the primary outcome will be tested between ethnic groups using an interaction term between randomised group and ethnicity in the main model. Separate subgroup analyses will also be conducted, and the results will be presented if equal recruitment targets are met.

Generalised linear regression models will be used to analyse secondary outcomes using a link function appropriate to the distribution of outcome variable. Similar model adjustments will be considered as in the primary outcome analysis. Model-adjusted group differences will be presented with 95% confidence intervals and p-values.

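### A Pacific participant who ticks none of the listed Māori or Pacific boxes, such as the SAP's own Tokelauan example, is classed as non-Māori/non-Pacific

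*SAP*

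**What the plan says.** SAP section 2.2 offers nine tick-all-that-apply options. Box (b) is Māori. Boxes (c) to (f) are Samoan, Cook Islands Māori, Tongan and Niuean. The last option, (i), is a free-text field worded "Other, e.g., Dutch, Japanese, Tokelauan (please state".

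The combined group is then defined by boxes alone: "Those who tick (b) and/or any of (c)-(f) will be in the ethnic group" Māori and/or Pacific. Those who do not "tick any of these options will be in the ethnic group" non-Māori/non-Pacific. The separate Pacific group used for summaries is limited in the same way: those who did not tick (b) but "ticked any of (c)-(f) will be in the ethnic group “Pacific".

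The two-way classification is used in several places:

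- Section 2.2: "These two categories are used to define the stratification factor “ethnicity” in randomisation". Section 1.5 confirms this: "Randomisation will be stratified by ethnicity (Māori and/or Pacific; non-Māori/non-Pacific) and alcohol use (light to moderate; heavy".
- Section 3.3 adjusts the primary model for it, and consistency of effect "will be tested between ethnic groups using an interaction term between randomised group and ethnicity in the main model".
- Section 3.2 gives separate baseline summaries by it and refers to it as part of the recruitment target.
- Section 3.3 presents separate subgroup results only if the equal recruitment targets are reached, and section 3.2 splits Māori from Pacific only if enough people are recruited.

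**The concern.** The group is labelled Pacific, but the rule admits only four named Pacific ethnicities. The form itself directs Tokelauan respondents to the free-text option, and the next sentence of the rule classes anyone with only that option as non-Pacific. The same would happen to any other Pacific ethnicity without its own box. Because the rule covers every respondent and assigns each to a class, this is a stated rule that gives a wrong answer, and not a detail left for another document.

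At stake is the one subgroup question that the SAP plans in advance. Some Pacific participants would sit in the comparison group, which pulls the two ethnic groups' estimated effects towards each other. They would also be counted towards the wrong recruitment target and left out of the Pacific descriptive tables. An analyst who noticed this at the end would have to follow a rule that is wrong for these people or depart from it without a prior plan.

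**Working it through.** **Step 1. Apply the section 2.2 rule literally.**

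| Boxes ticked | Class under the rule | Agrees with the group label? |
|---|---|---|
| (i) Tokelauan | non-Māori/non-Pacific | No |
| (a) and (i) Tokelauan | non-Māori/non-Pacific | No |
| (c) and (i) Tokelauan | Māori and/or Pacific | Yes |
| (b) and (i) Tokelauan | Māori and/or Pacific | Yes |

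The error is confined to Pacific participants who tick none of (b) to (f).

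**Step 2. Reproduce the plan's power figures (section 1.4).** Inputs: 1,000 participants, 250 per arm, 0.33 SD for the main comparison, 0.5 SD for the subgroup analysis, two-sided 5%. With SD = 1, power = Φ(d·√(n/2) − z), where n is the number per arm.

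- Main, Bonferroni for three comparisons (z = 2.394): 0.33 × √125 = 3.690, and Φ(3.690 − 2.394) = 90.2%. With a Dunnett critical value of about 2.35 it is 91.0%. Both agree with the stated figure of more than 90%.
- Subgroup, two equal ethnic groups, 500/4 = 125 per arm, unadjusted: 0.5 × √62.5 = 3.953, and Φ(3.953 − 1.960) = 97.7%. With three equal ethnic groups (about 83 per arm) it is 89.6%. The stated 90% is met or matched closely.

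These figures do not depend on how option (i) is coded.

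**Step 3. Dilution of the ethnic contrast.** The SAP does not say how many people are affected, so x is varied as an assumption. Take two ethnic groups of 500, filled by tick box, with x misplaced people in the non-Māori/non-Pacific group, spread evenly over the arms and responding to labels as the Māori and/or Pacific group does. With f = x/500, the estimated effect in the nominal non-Māori/non-Pacific group is (1 − f)·(its own effect) + f·(the Māori and/or Pacific effect). The contrast between the groups is therefore the true contrast times (1 − f).

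For one label against control, the interaction is a difference of two differences with 125 per arm in each group, so SE = √(4/125) = 0.179 SD. Power at two-sided 5%, unadjusted, is Φ(d/SE − 1.960). The true contrast is set at 0.5 SD for illustration.

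| x (assumed) | f = x/500 | Contrast, 0.5 × (1 − f) | Interaction power |
|---|---|---|---|
| 0 | 0% | 0.500 SD | 79.8% |
| 5 | 1% | 0.495 SD | 79.0% |
| 10 | 2% | 0.490 SD | 78.2% |
| 25 | 5% | 0.475 SD | 75.7% |
| 50 | 10% | 0.450 SD | 71.1% |

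**Step 4. Precision within the Māori and/or Pacific group.** If the target is filled by tick box, this group still reaches 500 and loses nothing. If the x people were instead missing and not replaced, it would have (500 − x)/4 per arm. Its unadjusted power for 0.5 SD would go from 97.7% to 97.6%, 97.5%, 97.1% or 96.3% for x = 5, 10, 25 or 50.

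**Step 5. The overall comparison.** The class depends only on baseline answers and the same rule serves all four arms. Allocation is random within the strata as defined, so adjustment for the stratum as defined leaves the label-versus-control difference unbiased.

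**The case against.** The best defence is that this is a small gap in a definition, with no bearing on the main result. Allocation happens inside the survey platform, where stratifying on boxes is practical and parsing free text is not. A stratum need not coincide with the final analysis category. The question allows several ticks, so some of the people in question will be classified correctly through another box. Option (i) asks for the ethnicity in words, so the information for a correction is already collected. The number affected is probably small, and at 1% to 2% the interaction loses less than two percentage points of power.

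Most of this stands, and it limits the point to a should-fix. It does not remove the point. The SAP uses the same box-only rule for the analysis categories as for the stratum, and nowhere says that the free text will be used.

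Three stronger readings are tempting and are not supported:

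- A reader might infer that the primary analysis is biased because ethnicity is a covariate in it. Step 5 shows that it is not.
- A reader might infer a substantial loss for the subgroup. That needs a number of Pacific participants and a share who use only option (i). The SAP gives neither.
- A reader might infer that the Māori and/or Pacific group itself is contaminated or short. Everyone in it ticked a qualifying box, and under a target counted by tick box it still fills. The contamination is in the other group.

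**Conclusion.** The concern holds in a limited form. Read as written, section 2.2 puts a Pacific participant who ticks none of (b) to (f) into non-Māori/non-Pacific, including one who gives the SAP's own example answer. It mislabels the ethnicity stratum, dilutes the interaction and subgroup contrast by about x/500, and miscounts Pacific participants in the descriptive tables and against the recruitment target, on which the reporting of separate subgroup results depends.

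The size rests on assumptions: two ethnic groups of about 500 (section 1.4 asks for roughly equal numbers but does not say whether it means two groups or three), a target counted by tick box, and an unknown x. Over the assumed 1% to 10%, the dilution is 1% to 10%, and the lower end is the more plausible. That Tokelauan is a Pacific ethnicity is general knowledge and is not stated in the SAP. The classification error itself is certain from the text. Only its size is uncertain.

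**What to change.** **Before launch:** add one Other Pacific tick box to the ethnicity question, with a free-text field. Include it both in the Māori and/or Pacific rule and in the rule for the separate Pacific group, and remove Tokelauan from the examples under option (i). The platform can then stratify correctly.

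**If the survey is already live:** the strata cannot be changed for those already randomised. Add a rule to section 2.2, fixed before unblinding, along these lines: *Free text under option (i) will be coded by someone blind to allocated arm and outcome. Participants who name a Pacific ethnicity will be classed as Māori and/or Pacific and, if they did not tick (b), as Pacific.* Use the recoded ethnicity for the interaction, the subgroup analyses and the descriptive tables. Keep the as-randomised stratum as the adjustment covariate in the primary model. The interaction model should also carry the main effect of the recoded variable. Report how many participants changed class, which supplies the missing x.

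The cost is one survey option and a line of text, or a short blinded recode of answers already collected. No sample-size figure changes.

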2.3. Primary outcome measure

Each participant will indicate how likely they are to purchase and drink the alcoholic drink, after viewing the product with or without the warning label in the group they are randomised to.

Their ‘likely intent’ to purchase and drink this alcoholic drink, is measured on an 11-point Juster probability scale, where zero represents “not likely at all to purchase and drink” and 10 represents “very likely to purchase and drink”.

(not likely at all)	(very likely to purchase)									
0	1	2	3	4	5	6	7	8	9	10

This outcome will be summarised as a continuous variable in analysis.

3. STATISTICAL ANALYSIS

All statistical analyses will be performed using SAS version 9.4 (SAS Institute Inc., Cary, NC, USA). All statistical tests will be two-tailed and at 5% significance level throughout the analyses.

Summaries of continuous variables will be presented as numbers observed, mean and standard deviations (SD), while categorical variables will be presented as frequencies and percentages. The amount of missing data will be reported. All results will be presented in a figure and tables based on the analyses stated below. The CONSORT 2010 statement will be used as the guideline for reporting.

3.1. Participant accountability

[figure not shown]
The number of participants who were registered, fulfilled eligibility criterion, together with reasons for exclusion will be summarised. The CONSORT diagram will be used to present the flow chart of all study participants (Figure 2).

3.2. Baseline characteristics

Baseline characteristics of all randomised participants will be summarised descriptively for each intervention and control groups. Since any differences between the groups at baseline could only have occurred by chance, no formal significance testing will be conducted.

As a pre-planned subgroup analysis that is considered in randomisation and the recruitment target, separate baseline summaries will be provided for Māori/Pacific and non-Māori/non-Pacific participants. If we recruit enough number of participants, all Māori and Pacific participants will also be summarised separately.

Figure 2: Participant flow diagram

3.3. Efficacy Analysis

Treatment evaluation will be performed on the principle of intention-to-treat (ITT), including all randomised participants in the group they were randomised to. Since all eligible participants will receive the intervention and complete the questionnaire online, no per protocol analyses are planned.

The primary outcome will be analysed using linear regression model, adjusting for stratification factors (ethnicity and alcohol use) and the type of alcohol the participant chose (beer, wine, spirit or RTD), and controlling for multiple comparisons with the control group. Other baseline characteristics (e.g. sex and age group, pre-existing alcohol-related health conditions) will be considered in the model if deemed important. Model-adjusted mean difference between the groups will be estimated with 95% confidence interval and p-value.

As a pre-planned subgroup analysis, the consistency of intervention effects on the primary outcome will be tested between ethnic groups using an interaction term between randomised group and ethnicity in the main model. Separate subgroup analyses will also be conducted, and the results will be presented if equal recruitment targets are met.

Generalised linear regression models will be used to analyse secondary outcomes using a link function appropriate to the distribution of outcome variable. Similar model adjustments will be considered as in the primary outcome analysis. Model-adjusted group differences will be presented with 95% confidence intervals and p-values.

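### The baseline weekly number of drinks purchased is collected but pre-specified in no model, and the primary model's covariate list is left open

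*SAP*

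**What the plan says.** Section 3.3 of the SAP analyses the primary outcome (the 0-10 intent scale) by linear regression. It adjusts for the two stratification factors, ethnicity and alcohol use, and for drink type. It then adds: "Other baseline characteristics (e.g. sex and age group, pre-existing alcohol-related health conditions) will be considered in the model if deemed important". The secondary outcomes get generalised linear models, for which adjustments along the same lines are to be considered. The ethnicity interaction is tested within the main model, so it inherits whatever covariate set that model ends up with.

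The baseline questions in section 1.7 include purchase quantity: "Participants will be asked to estimate their average, weekly number of alcoholic drinks purchased from an off-license retailer". Among the secondary outcomes, section 1.8 first lists the participant's imagined regular weekly shop, in which they "choose how many (from a drop-down menu of 0-100) of this particular alcoholic drink they would buy and drink". No model in section 3.3 names the baseline number.

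Alcohol use enters the model as the randomisation stratum. Section 2.1 calculates a total AUDIT-C score out of 12 and cuts it in two, heavy use being an "AUDIT-C score of ≥ 3 for women and ≥ 4 for men".

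**The concern.** How many drinks a person says they would buy in a regular weekly shop should depend heavily on how many they usually buy. If the analysis leaves that usual number out, differences between people stay in the residual and the label effects on purchase number are estimated less precisely than the collected data allow.

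The second issue is the open clause in the primary model. The examples it gives are not a closed list, and it does not say what counts as important, who decides or when. Section 1.6 keeps the investigators and the trial statistician blinded until the end of the trial, but the SAP does not say that the covariates are chosen while that blinding lasts. As written, the primary estimate, the ethnicity interaction and the secondary estimates could all depend on a choice made with the outcome data by group in view.

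**Working it through.** **1. The plan's own power figure.** Section 1.4 claims more than 90% "power at the 5% overall significance level (two-sided) to detect an effect size of 0.33 Standard Deviations (SD) on the primary outcome". The claim is for a single label against control, after a multiplicity adjustment, at 250 per arm. The adjustment method is not named, so I take Bonferroni for three comparisons.

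- Critical value: z(1 − 0.05/6) = 2.3940.
- Standardised difference: 0.33 / √(2/250) = 3.690.
- Power: Φ(3.690 − 2.394) = Φ(1.296) = 90.2%.
- Size needed for 90%: 2 × (2.3940 + 1.2816)² / 0.33² ≈ 248.1, so 249 per arm.

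With a Dunnett critical value of 2.348 the power is 91.0%. The stated figure reproduces, and no covariate gain is needed to reach it.

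**2. Possible gain for the primary outcome.** Let R² be the extra outcome variance explained by added covariates. The SAP gives no value, so 0.05 and 0.20 are assumptions. The residual SD becomes √(1 − R²).

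- R² = 0.05: 3.690 / 0.975 = 3.785; Φ(3.785 − 2.394) = 91.8%; intervals 2.5% narrower.
- R² = 0.20: 3.690 / 0.894 = 4.125; Φ(4.125 − 2.394) = 95.8%; intervals about 11% narrower.

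**3. Possible gain for the purchase-number outcome.** Let r be the correlation between usual and intended quantity (assumed 0.5-0.7). On a linear scale the residual variance is multiplied by 1 − r².

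- r = 0.5: 0.75, a 25% reduction; √0.75 = 0.866, intervals 13% narrower.
- r = 0.7: 0.51, a 49% reduction; √0.51 = 0.714, intervals 29% narrower.

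These are upper figures, because the alcohol-use stratum already takes up part of this variance. To illustrate, assume the stratum correlates 0.35 with the outcome and 0.5 with baseline quantity. The squared partial correlation is (r − 0.35 × 0.5)² / [(1 − 0.35²)(1 − 0.5²)] = (r − 0.175)² / 0.658.

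- r = 0.5: 0.325² / 0.658 = 0.16.
- r = 0.7: 0.525² / 0.658 = 0.42.

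The further reduction is then about 16-42%.

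**4. What the two-level alcohol factor keeps.** If the AUDIT-C score were normal and linearly related to the outcome, a cut leaving a share p below it would keep φ(z_p)² / [p(1 − p)] of the variance that the full score explains: 64% at p = 0.5, 49% at p = 0.2 and 34% at p = 0.1. The SAP does not give the share.

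**5. Ceiling on the effect of free covariate choice.** A simulation with no true effect used four arms of 250, Bonferroni at 0.05/3, five independent optional covariates and 3,000 runs per setting. In each run the smallest p-value over all 2⁵ = 32 covariate subsets was kept. The family-wise error was 5.4%, 7.6%, 12.7% and 16.4% for a per-covariate R² of 0, 0.02, 0.05 and 0.08. With a fixed model it was 4.0-4.7%.

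**The case against.** Four things can be said in support of the plan.

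- **Nothing is excluded.** The list in section 3.3 is illustrative, so baseline quantity could still be used. This is correct: the variable is not barred, only not pre-specified. A SAP is the place to settle that.
- **The counterpart is not exact.** Section 1.7 asks about all off-licence alcoholic drinks, while section 1.8 asks about the one drink shown. This stands. It makes the correlation uncertain, but baseline quantity is still the nearest measure available.
- **The variance figures are assumed.** They rest on a chosen correlation and a linear formula, which does not carry over directly to a count model. This also stands, so the figures are indicative and apply to a secondary outcome only.
- **Blinding limits abuse.** Section 1.6 helps if the covariates are settled before unblinding, but the SAP does not say so. The gap is narrowed, not closed.

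A reader might also infer that AUDIT-C has been left out. It has not: section 3.3 adjusts for alcohol use, which section 2.1 derives from AUDIT-C, and only the finer score is lost. Nor do the documents show that the cut separates few people. By the scoring in section 2.1, a woman having 1 or 2 drinks 2-3 times a week scores 3 + 0 + 0 = 3 and is classed as heavy. But a woman having 1 or 2 drinks 2-4 times a month, and never six or more, scores 2 + 0 + 0 = 2 and falls below the cut. Both can meet the past-week eligibility rule.

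**Conclusion.** The point holds as a specific, inexpensive improvement. A baseline measure close to the purchase-number outcome is collected and assigned to no model, and the primary model's covariate set is not closed.

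For the purchase-number outcome the gain is up to 25-49% lower residual variance at an assumed correlation of 0.5-0.7, and less after the existing covariates. For the primary outcome it may be small: power rises from 90.2% to 91.8-95.8% at an assumed extra R² of 0.05-0.20.

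Two stronger readings are not supported. The trial is not underpowered for want of these covariates, because its stated power is met without them. Nor should an error rate of 7.6-16.4% be expected: that range is a worst case which requires choosing the covariate set by the treatment p-value, and nothing in the SAP suggests this is intended. The open clause on its own is mainly a missing detail, worth closing because doing so is cheap.

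**What to change.** In section 3.3:

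1. Pre-specify the baseline weekly number purchased as a covariate in the purchase-number model, suitably transformed, for example log(x + 1).
2. Replace the open sentence on other baseline characteristics with a closed covariate list for the primary model: the two strata, drink type and named baseline variables such as age group and sex. State that the list is fixed before unblinding.
3. Label any model with a different covariate set as a sensitivity analysis.

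Adding the total AUDIT-C score beside the alcohol-use stratum is optional, since alcohol use is already adjusted for in two-level form.

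The cost is a few lines of SAP text and a few degrees of freedom out of about 1,000. No new data are needed.

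### Presentation of the separate ethnic subgroup estimates depends on an undefined equal-recruitment condition that the validity of those estimates does not need

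*SAP*

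**What the plan says.** SAP section 3.3 plans two ethnic analyses of the primary outcome. The first is a test of the interaction between randomised group and ethnicity in the main model, with no condition on reporting it. The second is the pair of within-group analyses: "Separate subgroup analyses will also be conducted, and the results will be presented if equal recruitment targets are met".

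The ethnic comparison is part of the design. Section 1.5 stratifies randomisation by two ethnic categories, Māori and/or Pacific and non-Māori/non-Pacific, and section 2.2 defines them. Section 3.2 introduces the ethnic summaries with "As a pre-planned subgroup analysis that is considered in randomisation and the recruitment target". Section 1.4 gives the subgroup its own power statement: "An approximately equal sample size per ethnic group will provide 90% power at 5% significance to detect a group difference of 0.5 SD".

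The SAP states no figure for the recruitment target in each ethnic group, no margin within which the groups would count as equal, and no forecast of the split.

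**The concern.** The within-group analyses are always run; only their disclosure is conditional. Three features make the condition a poor one.

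- It is undefined. Section 1.4 works with "An approximately equal sample size per ethnic group", while section 3.3 drops the qualifier. Whether 460:540, say, meets the condition is left to someone's later judgement.
- It is not needed for validity. Stratified randomisation protects the label-control comparison inside each ethnic group at any group size.
- It separates results that belong together. The interaction p-value would be reported while the estimates a reader needs to interpret it could be held back, for the larger group as well as the smaller.

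At stake is whether the label effect in Māori and/or Pacific participants, a group the trial stratifies on and powers for, is published if that group is under-recruited.

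**Working it through.** **Inputs from the SAP.** Section 1.4: "A sample size of 1,000 participants (250 per arm"), testing "at the 5% overall significance level (two-sided"), the main target "to detect an effect size of 0.33 Standard Deviations (SD) on the primary outcome", and the comparison "between any one of three label groups and the control, with adjustment for multiple comparisons". The subgroup target is 0.5 SD with 90% power at 5%. Section 1.5 gives 1:1:1:1 allocation and two ethnic strata.

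**Assumptions.** SD = 1; total fixed at 1,000; arms equal within each ethnic group, so n per arm = group total / 4; no gain from covariates. The SAP does not name its multiplicity method, so results are shown unadjusted (critical value 1.960) and with Bonferroni for three comparisons (2.394). The splits are illustrative.

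**Formulas.** Power = Φ(d/√(2/n) − critical value). Unadjusted 95% half-width = 1.96 × √(2/n).

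**The plan's own figures.**
- Main comparison, n = 250, d = 0.33: 0.33/√(2/250) = 3.690, and Φ(3.690 − 2.394) = 90.2% with Bonferroni. With Dunnett (simulated critical value 2.35) it is 91.0%. The stated power above 90% reproduces.
- Subgroup, two equal groups of 500, n = 125, d = 0.5: 0.5/√(2/125) = 3.953, giving Φ(1.993) = 97.7% unadjusted and Φ(1.559) = 94.0% with Bonferroni. The stated 90% is exceeded.
- Subgroup, three equal groups of about 333, n ≈ 83, unadjusted: 89.7%, which matches the stated 90%. The SAP does not say which grouping the figure refers to.

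**Smaller of two groups, d = 0.5.**

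| Split | n per arm | d/√(2/n) | Power, unadjusted | Power, Bonferroni | Half-width (SD) |
|---|---|---|---|---|---|
| 50:50 | 125 | 3.953 | 97.7% | 94.0% | 0.248 |
| 60:40 | 100 | 3.536 | 94.2% | 87.3% | 0.277 |
| 70:30 | 75 | 3.062 | 86.5% | 74.8% | 0.320 |
| 75:25 | 62.5 | 2.795 | 79.8% | 65.6% | 0.351 |

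The t distribution gives slightly lower power: 94.0% and 86.8% at 100 per arm, 86.0% and 73.8% at 75 per arm.

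**Where 90% is lost.** n = 2 × ((critical value + 1.282)/0.5)², rounded up, is 85 per arm unadjusted (340 in the group) or 109 with Bonferroni (436 in the group). With two groups, the stated 90% therefore survives to about 34:66 unadjusted, or 44:56 with Bonferroni.

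**Larger group.** At 60:40 it has 150 per arm: Φ(0.5/√(2/150) − 1.96) = 99.1% unadjusted. Its estimate becomes more precise, yet the condition could withhold it too.

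**Interaction test.** For a 0.5 SD difference between groups in one label's effect, the standard error is √(2/n₁ + 2/n₂). Power is 79.8% at 500/500, 78.2% at 400/600 and 72.6% at 300/700. The result that is always reported is thus the less powerful one for a difference of 0.5 SD.

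**The case against.** The best defence is that the trigger is a recruitment count written down in advance, not an effect estimate or a p-value. Ethnicity is collected before randomisation, and section 1.6 keeps investigators and statistician blinded until the end of the trial. This stands: a reader might infer that results are to be shown or hidden according to what they look like, and the SAP does not say that. What remains is that no tolerance is fixed, and nothing requires the judgement on equality to be made before the subgroup results are seen.

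Other limits also stand.

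- A reader might infer that a shortfall is likely. The SAP gives no forecast or expected split, so it supports no such statement.
- A reader might infer that the withheld analysis would always be well powered. That holds for moderate shortfalls with two groups. It fails at 75:25, and it has no margin if the 90% was meant for three groups.
- A reader might infer that all ethnic subgroup results are suppressed. The interaction test is unconditional, and so are the section 3.2 baseline summaries for the two main groups.
- Section 3.3 says if, not only if, and its equal target may be shorthand for the approximate one in section 1.4. The restrictive reading is the natural one, but the text should not depend on it.

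Stating a numerical tolerance would cure the vagueness. It would still withhold valid estimates whenever the number was missed. Low power is a reason to show a wide interval with a caution, not to omit it.

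**Conclusion.** The point holds as a reporting defect in a pre-planned analysis; the primary analysis is unaffected. Section 3.3 makes disclosure of the separate ethnic estimates depend on a condition that the SAP does not define and that the within-group comparisons do not need. The precision at stake is moderate: the smaller group's half-width grows by about 12% at 60:40 (0.277/0.248) and 29% at 70:30 (0.320/0.248). These sizes rest on two ethnic groups, 1,000 participants and assumed splits. The argument for presenting the estimates does not rest on them, because validity follows from the stratified randomisation in section 1.5 and the interval shows whatever precision is achieved.

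**What to change.** In section 3.3, delete the equal-target condition and state that label-control differences, with group sizes and 95% confidence intervals, will be presented for both Māori/Pacific and non-Māori/non-Pacific participants whatever numbers are recruited, alongside the interaction p-value. Add that lower precision will be noted if one group falls short.

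The separate analyses already planned can supply these estimates. There is no need to replace them with estimates from the interaction model, or to add separate Māori and Pacific effect estimates.

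The cost is a short change to the SAP text and no new data. The downside is a wider interval in the smaller group, which readers must be told to interpret with care.
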